### 5.2 Data and Sample Sharing Plan

CNS IRB Protocol Template (2.5.15)

Results of genetic tests obtained at NIH are often preliminary and difficult to interpret because the testing is being done for research purposes only and the laboratories are not clinically certified. Results will not be shared with participants, their families, or insurance companies.

Blood samples that are not analyzed at the NIH Clinical Center will be transferred to the CNRM Biospecimen Repository (USUHS Protocol No. CNRM-004 "Biorepository and Informatics Warehousing") for storage and materials will be shipped in accordance with NIH and federal regulations. Data will be transferred to CNRM Informatics Data Repository (CNRMIDR-001). No personally identifiable data will be transferred to CNRM. A global unique identifier (GUID) that is not linked to any personal identifiers will be generated for each participant and be used to share samples with CNRM. A materials transfer agreement will be put in place before any transfers are made.

# 6. Risks and discomforts

# 6.1 Risks of Exercise Training

The risks of this study are those associated with participation in vigorous aerobic exercise. The general risks of exercise include myocardial infarction, angina, shortness of breath, dizziness, early onset of fatigue and exhaustion, joint or muscle pain and numbress. Many of these symptoms may occur during the immediate post-exercise recovery phase, which is generally thought to be the first six minutes following strenuous exercise.

Many subjects will experience delayed onset muscle soreness after the exercise tolerance tests or after the exercise-training phase. This soreness will be mild to moderate in intensity and could begin immediately after exercise or up to 48 hours following the exercise session. It will typically subside within a seven-day period. Continued participation in exercise training does not appear to increase or prolong delayed muscle soreness. Many subjects will also experience increased levels of fatigue that are sustained for up to 24 hours following the exercise sessions. This fatigue will typically subside after one to three weeks.

The most serious risks for those participating in exercise are cardiovascular abnormalities. These risks are slight even in individuals with known severe coronary atherosclerosis during exercise tolerance testing. In studies that include patients with known heart disease as well as patients in whom the presence of heart disease is unknown, morbidity and mortality during maximal exercise testing remains low at 0.0 to 8.3 per 100,000 and 0.0 to 1.0 per 100,000 respectively [33-42]. Morbidity and mortality remain at similar lows for maximal exercise testing environments that are attended by a physician and those supervised by a physician but conducted by qualified physician extenders [34, 37, 40, 43, 44]. Exercising at submaximal intensities, such as during AET, carries with it even lower risk of adversity.

To minimize risk and maximize safety, all exercise tests will be carried out in laboratories that are in the NIH Clinical Center with immediate response backup. All subjects will be screened by medical history and medical examination to exclude those with contraindications to exercise in whom testing and training might be unsafe. Subjects will be monitored during the treadmill exercise tests by 12-lead EKG. Subjects will be informed of the signs and symptoms of heart disease and questioned frequently during the test regarding the presence of symptoms of heart, neurological, or musculoskeletal conditions. An infographic (Appendix 14) for the common warning signs of a heart attack will also be available for subjects. As recommended by the American Heart Association and the American College of Sports Medicine, exercise will be overseen by personnel appropriately trained to extend physician services in the form of exercise testing and training in the clinical setting [45]. People with TBI comorbid with severe systemic illnesses will not be participants. The investigators and clinical exercise training and testing staff in our laboratory are highly experienced in treadmill cardiorespiratory testing, even in high-risk patients such as those with congestive heart failure and pulmonary artery hypertension.

TBI is not thought to increase cardiovascular risk or the risk of life-threatening adverse events during treadmill testing. According to the American College of Sports Medicine, subjects in this study will be classified as low or moderate risk for adverse events [45]. Recommendations for this classification are that physical examination is not necessary for low risk subjects prior to participation and physician supervision of a peak or submaximal exercise test is not necessary. In contrast, for moderate risk participants, a pre-training physical examination and physician supervision of a maximum exercise test is recommended, although physician supervision of a submaximal test is not necessary in the moderate risk group according to ACSM recommendations. However, RMD operating procedures are that a physician is in close proximity (in the department) at all times during an exercise test. This policy meets the definition of physician supervision in the ACSM guidelines [45]. In addition, all subjects will receive a physical examination, including the pre-participation history and physical exam parameters recommended by the ACSM [45]. All of the investigators and laboratory personnel are clinical exercise professionals certified by the ACSM, physical therapists, laboratory personnel certified and credentialed in the RMD exercise laboratory, or rehabilitation medicine physicians. All are trained in basic life support. Rapid code team response is readily available for the RMD Exercise Testing Laboratory and Fitness Center. All treadmill testing and elliptical training procedures will rigorously conform to ACSM guidelines and stopping points [45] (Appendix 11).

### 6.2 Risk of Treadmill or Elliptical Use

Risk of injury also includes those related to falling on a moving treadmill belt, such as abrasions, contusions, cuts, sprains, and fractures. The likelihood that any of these injuries would occur is small and preventive measures will be enforced to insure that the risks remain at a minimum.

The treadmill is equipped with handrails for aiding balance and providing increased stability. The treadmill also is equipped with a "hot" switch that is easily within the reach of the subject while walking on the treadmill. When the switch is activated, the treadmill stops and ends the test immediately. Under this circumstance the treadmill cannot be restarted unless both the treadmill itself and the computer control are reset. Subjects are instructed in treadmill safety and the use of the hot switch before beginning

the test protocol. Subject response to the test is monitored visually, electronically, and by verbal interaction between the subject and the testing staff.

Risk of injury with the use of an elliptical machine includes falling off or tripping caused by slippage off the pedals. Moving parts also create potential pinch hazards. There may also be feet, ankle and back discomfort if subjects are unused to the motion. The likelihood of these injuries occurring is minimal and proper form and familiarity with the device would reduce these risks further. Also sessions will be closely monitored by credentialed personnel and subjects will be asked for feedback during the exercise session.

### 6.3 Risk of Motor and Balance Assessments

There is a slight risk of falls especially in those with TBI since we are challenging their motor capabilities, but should be no greater than those encountered in everyday life. A harness will be used during balance testing and the examiner will closely guard the patient. The adhesive tape that will be placed on the skin may cause mild skin irritation or discomfort upon removal.

Stand-by assistance by a physical therapist or a safety belt or overhead harness will be used whenever there is a potential for unsteadiness that could lead to a fall during the motor and balance tests, or if the patient is concerned about falling.

### 6.4 Risk of Neuropsychological Testing and Questionnaires

The neuropsychological tests are not harmful, but may be frustrating or stressful. Filling out the questionnaires may be perceived as boring.

If the participant experiences distress, anger or any other emotional or behavioral symptoms during the neuropsychological tests, [name] will assess the situation and make recommendations or referrals as needed. All subjects will be informed prior to consent that they will be asked multiple questions that relate to their emotional and psychological health, and they will be told that they can refuse to answer any or all questions that they are not comfortable with. They may also stop the testing at any time for any reason.

### 6.5 Risk of MRI

People are at risk for injury from the MRI magnet if they have pacemakers or other implanted electrical devices, brain stimulators, some types of dental implants, aneurysm clips (metal clips on the wall of a large artery), metallic prostheses (including metal pins and rods, heart valves, and cochlear implants), permanent eyeliner, implanted delivery pump, or shrapnel fragments. Welders and metal workers are also at risk for injury because of possible small metal fragments in the eye of which they may be unaware. It is not known if MRI is completely safe for a developing fetus and therefore will not be done if the subject is pregnant. People with fear of confined spaces may become anxious during an MRI. Those with back problems may have back pain or discomfort from lying in the scanner. The noise from the scanner is loud enough to damage hearing, especially in people who already have hearing loss. Another risk is boredom in the MRI since

CNS IRB Protocol Template (2.5.15)

subjects will be asked to lie quiet and still for several minutes at a time. There are no known long-term risks of MRI scans.

All subjects will be screened for MRI contraindications before each scan, and if any are present, will not receive an MRI scan. In addition, all magnetic objects (for example, watches, coins, jewelry, and credit cards) must be removed before entering the MRI scan room. The scan will not be done on anyone who is pregnant. A pregnancy test will be done on all female subjects who have the possibility of being pregnant within 24 hours of having each MRI. Everyone having a research MRI scan will be fitted with hearing protection.

### 6.6 Risk of Blood Draw

Needle punctures for drawing blood usually do not cause any serious problems. However, drawing blood may cause pain and carries a small risk of bleeding, localized bruising, discomfort and/or infection at the injection site, or temporary dizziness. If any of these occurs, they will be treated. The study will draw no more than 120 mL of blood for the entire study, which is below the maximum amount of blood that can be drawn as required by NIH guidelines which is no more than 450 mL in any 6 month period.

### 6.7 Risk of EKG

There is minimal medical risk or discomfort from the EKG.

### 6.8 Risk Associated with Hypercapnic Challenge

Some of the side effects of early hypercapnia include flushed skin, increased heart rate, muscle twitches, hand flaps, and possibly elevated blood pressure. Severe hypercapnia can also cause disorientation, headaches, panic, hyperventilation, and unconsciousness. Symptoms disappear with the resumption of breathing regular room air. The hypercapnic challenge used is of short duration and very mild, and the subject will be monitored closely during this challenge for discomfort and symptoms. The subject will be immediately switched back to room air at the subjects request or if staff detect excessive subject discomfort.

### 6.9 Risks of Sharing Research Data

Samples and data provided to the CNRM Biospecimen Repository (CNRM-004) and CNRM Informatics Data Repository (CNRMIDR-001) will be coded using a Global Unique Identifier (GUID) derived from PII and generated locally. Re-identification of data and samples collected at the NIH would be possible if repository data and samples are released with the GUID to other CNRM investigators who have access to the same subjects PII through participation in other IRB approved studies as they will generate the same GUID at their site. Re-identification is unlikely, however, as the CNRM Repository intends in most cases to release data and samples without the GUID.

The following measures will be made to minimize breach of confidentiality of records or data:

• All research procedures will be conducted by staff qualified to perform the procedure and with monitoring as defined in sections 7 and 10.

• Confidentiality will be protected as described in Section 19.

• Use of subject data that is re-identified through PHI used to generate a GUID is permitted only under IRB approved protocols with pre-defined research questions.

# 7. Subject Safety Monitoring

### 7.1 Parameters to be Monitored

*Motor Assessment:* All motor and balance assessments will be performed in the Functional & Applied Biomechanics Section under closely monitored conditions. A clinically credentialed staff member will remain with the subject at all times to ensure their safety and to assist them as needed. Subjects will be instructed to tell us if any of the tests are uncomfortable or concern them in any way. The primary parameters we will be monitoring are dizziness, unsteadiness, fatigue, or any indication that they are becoming distressed during the testing.

*MRI*: The subject will be in voice contact with MRI staff at all times during the scans and we will respond to their questions or concerns as needed. On site medical personnel and emergency medical assistance will be available for all MRI studies.

*Treadmill CPET:* All of the CPET tests will be performed in the RMD exercise testing laboratory in the Hatfield Clinical Research Center under closely monitored conditions. Clinically credentialed staff members will perform and monitor the tests and recovery period to ensure safety and assist the subjects as needed. Accepted clinical credentials are ACSM certification as a Clinical Program Director, Registered Clinical Exercise Physiologist, or Clinical Exercise Specialist, Licensed Physical Therapist, Licensed Physician, or individuals declared competent for administering exercise training and testing by the RMD. As part of their credentialing, staff members are knowledgeable in exercise test EKG monitoring and endpoints and will monitor EKG and blood pressure responses during the tests. The treadmill is equipped with handrails for aiding balance and providing increased stability to avoid risk of falling.

*Exercise Training:* Exercise training will be conducted on elliptical machines located in the RMD's Fitness Center, Exercise Testing Lab or Functional & Applied Biomechanics Lab. A clinically credentialed individual will monitor and record adherence to the target heart rate and session duration guidelines, changes in medications should they occur, exertional symptoms should they occur, and attendance. Supervision by the clinically credentialed individual will take place in the same room as the participant.

Severe Depressive Symptoms and/or Suicidal Ideation: Physicians and study staff in this study will monitor subjects throughout the protocol procedures. Physicians and study coordinator or other research staff member will be with the participant and will monitor for any anxiety and will assess any issues that arise such as suicide ideation. Procedures are done at the NIH Clinical Center and medical emergency services are available to participants in this study, if needed.

### 7.2 Criteria for Stopping Procedures

*Treadmill CPET:* Subjects will be reminded of test stopping points and exertional symptoms and will be queried by the staff frequently during the tests regarding their presence. While volitional exhaustion is the target test endpoint on the CPET, other stopping points are those recommended by the ACSM [45] (Appendix 11).

### 7.3 Criteria for Individual Subject Withdrawal

Federal regulations require that subjects may withdraw from participation in the study at any point without prior notice and without adversely affecting their medical management, educational or employment status. At the time of withdrawal, subjects will also be able to withdraw their data from the study. The study investigators may also withdraw subjects from the study for medical, administrative or issues of non-compliance. If the subject experiences a clinically significant worsening of mood or behavioral symptoms (not an emergency), she/he will be removed from the study and the physician and/or neuropsychologist will ask the subjects if they would like them to make a referral for further outside evaluation and treatment. Any psychiatric emergency would also be cause for withdrawal from the study and will prompt immediate psychiatric evaluation at NIH.

During the course of the study, subjects will be instructed to continue with their current care. Alterations of care must not include changes in therapy, exercise regimen or medication that would potentially alter cardiorespiratory capacity, mood, or cognitive or motor abilities, or the ability to achieve a training adaptation measurable by the methods used in this study. If the subject does make these types of changes, they will be administratively withdrawn from the study. If a subject misses an assessment and is unable to reschedule it within four weeks, they will be withdrawn from the study. We will replace all who withdraw or were withdrawn from the study for the above reasons.

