# Precis

# Objective

The broad objective of this study is to examine the effects of moderate and more intense aerobic exercise as an intervention on cognitive performance, physical functioning and health-related quality of life in patients with chronic (more than 12 months post-injury) traumatic brain injury (TBI). Importantly, structural and biological brain changes will be measured to examine whether functional outcomes are related to exercise-induced adaptations. It is hypothesized that in the chronic phase of persons with TBI, there will be improved: 1) cognitive function, 2) physical fitness and fatigue severity, 3) motor performance and balance, and 4) mood and depressive symptoms, in those that performed the exercise intervention compared to a control group. It is also hypothesized that these functional improvements will be related to exercise intensity, improved cortical connectivity, dopamine transmission gene scores, and blood biomarkers related to neuroand angio-genesis.

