# **Outcome Measures**

Cognitive performance will be tested and interpreted compared to norms. Performance on motor and balance tasks will be assessed with the Smart Balance Measurement System and the GAITRite System. Physical fitness will be determined by peak oxygen consumption and aerobic threshold as measured by pulmonary gas exchange during an exercise tolerance test on the treadmill. Structural brain volumes will be determined by magnetic resonance imaging (MRI) and cortical connectivity will be quantified using resting state functional MRI and Diffusion Tensor Imaging (DTI) to evaluate integrity of and changes in white matter tracts in response to exercise and compared to healthy

CNS IRB Protocol Template (2.5.15)

volunteers. Blood will be collected to quantify the presence of biomarkers (such as VEGF, BDNF and IGF-1) and dopamine transmission, and compared to healthy volunteers. Other self-reported measures of quality of life, fatigue severity, depression and sleep quality would also be collected, and compared to healthy volunteers.

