### 8.2 Secondary Outcomes

Secondary outcome measures included here are those which have been shown previously or that we hypothesize to improve as results of exercise. Analysis will include comparisons of both exercise groups both combined and separately to the control group, and pre- to post-intervention changes within and across exercise groups in the following:

• Changes in other measures of cognitive function as measured by the

neuropsychological assessments

- Changes in motor assessments including balance and reaction time to perturbations
- Changes in cardiorespiratory fitness as measured by peak VO2 achieved and time on the treadmill
- Change in fatigue severity as measured in the FSS; other quality of life, physical activity, and sleep quality scales will be used to enhance interpretation of the FSS findings
- Changes in MRI findings, both structural and functional measures; e.g., increases in hippocampal brain volume, or increases in the degree of functional connectivity or fractional anisotropy between brain regions that sub serve motor, cognitive and behavioral functioning.
- Changes in biomarkers

We are also interested in examining relationships among various outcomes (functional, behavioral, structural, mechanistic, etc.) in persons with TBI. Therefore, secondary analyses may include correlations or comparisons of baseline measures within and across the groups. Comparisons of outcome measures including blood biomarkers, brain imaging, neuropsychological and questionnaire data will also be made to a reference healthy volunteer sample that is matched for sex and age within 5 years.

Table 4.	Summary	of t	the	Relevant	Outcome	Variables	for	the	Secondary	Outcome
Measures										

Test/Construct Measured	Relevant outcome variable
Gait Speed	Free and fast walking velocity
Dual Task Performance	Cognitive and motor cost (difference between DT and ST performance)
LOS/Dynamic Balance	Reaction time, maximal excursion
Elliptical Speed (reciprocal coordination)	Free and fast cadence on the elliptical
SOT/3 sensory systems	Equilibrium score for each sensory system
MCT/involuntary reaction time	Mean latency of responses
Adaptation/stability when perturbed	Sway velocity in 2 conditions

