# 9. Statistical Analysis

### 9.1 Analysis of data

The primary analysis is a mixed model (with time as the within-subject factor and exercise group as the between subject factor) analysis of variance (ANOVA) which will be used to determine significant differences in the primary (ANOVA) and secondary outcome variables (MANOVA by outcome category – i.e. motor, cognitive, behavioral, etc – to help control for multiple comparisons) as a result of exercise. Therefore, the data will include the time points immediately pre and post exercise for all subjects. We are interested in both main effects for time and exercise as well as potential interaction effects between exercise group and time.

All subjects completing the protocol and not withdrawing or presenting off study criteria will be included in the analyses. Secondary analyses related to protocol adherence and other aspects of feasibility are anticipated. Estimation of the necessary and sufficient sample size was calculated for a large effect change in the main outcome variable, pre- to post-training change in executive functioning. Significance will be set at p < 0.05.

While we do not anticipate that subjects will improve over time in the absence of exercise, we have included a waitlist control to evaluate this, and we will compare the amount of change over time in the control group versus the exercise group that were not waitlisted using an independent t-test. Also for the exercise group that was not waitlisted, there will be a three month follow up period evaluated to determine whether there is any change compared to the end of the exercise period using paired t-tests.

The change in aerobic capacity and fast elliptical speed will be correlated with changes in the other outcomes measures. Baseline dopamine transmission scores will also be correlated with all motor outcomes using linear regression.

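### Subjects removed for worsening mood or behaviour are replaced and left out of the analysis, so the mood and behavioural outcomes are analysed in a set selected on a closely related construct

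*Combined protocol and SAP*

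**What the plan says.** Section 7.3 sets the removal rule: "If the subject experiences a clinically significant worsening of mood or behavioral symptoms (not an emergency), she/he will be removed from the study". A psychiatric emergency is also a cause for withdrawal. No instrument or threshold is named. The same section adds: "We will replace all who withdraw or were withdrawn from the study for the above reasons". Section 3.1 repeats the replacement rule, aiming for at least 20 subjects per group at the second assessment.

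Section 9.1 defines the analysis set: "All subjects completing the protocol and not withdrawing or presenting off study criteria will be included in the analyses". The document provides no follow-up after removal, no all-randomised analysis and no sensitivity analysis for these subjects.

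Mood is an outcome. The fourth hypothesis in the Precis (Objective) is improvement in "mood and depressive symptoms, in those that performed the exercise intervention compared to a control group". The Precis (Outcome Measures) adds: "Other self-reported measures of quality of life, fatigue severity, depression and sleep quality would also be collected". The BDI-II and BSI-18 are collected (section 4.4.2), questionnaire scores are listed as outcome variables with Table 4, and section 9.1 names a behavioural category for MANOVA. The bullets in section 8.2 do not name mood.

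Two kinds of test are planned. Section 8.2 includes "pre- to post-intervention changes within and across exercise groups in the following". For the mixed model in section 9.1, "the data will include the time points immediately pre and post exercise for all subjects", and "We are interested in both main effects for time and exercise as well as potential interaction effects between exercise group and time". Separately, section 9.1 compares change in the wait-list with change in the initially exercising subjects by an independent t-test.

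**The concern.** The removal rule runs in one direction: worsening takes a subject out, improvement does not. Replacement restores the head count but not the missing outcomes. The completers' mood scores are therefore a sample from which part of the bad tail has been cut.

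The time effect is the most exposed. The mixed model uses each subject's own pre- and post-exercise visits, including the wait-list subjects' later training period, so its time effect has no concurrent unexercised control to cancel the cut. Its bias has a known direction, toward improvement.

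The between-group comparisons are less exposed, but they shrink when there is a real effect. If exercise helps mood, fewer exercisers are removed and the wait-list contrast understates the benefit. If one intensity worsens mood, more of that group are removed and the AET-versus-RET contrast understates the harm. At stake is a report of mood improvement, or of no mood harm, that leaves out the people whose mood clinically worsened.

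**Working it through.** **Inputs from the documents.** Section 9.2: 80 recruited for 60 completers, so 80 − 60 = 20 losses from all causes. Section 9.1: significance at 0.05. Section 4.4.2: eight questionnaires, of which BDI-II and BSI-18 are taken here as the two mood scales.

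**Inputs assumed, because the documents give none.** The proportion p removed for mood or behaviour: 2%, 5% or 10% (1.6, 4 or 8 of 80; 8 would be 8 of the 20 expected losses, a high case). The correlation r between the clinical worsening that triggers removal and change on a scale: 0.5, with r = 1 as a ceiling. The correlation between scales: 0.5.

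**Model.** Scale change D is standard normal, positive meaning worse. Clinical worsening is L = rD + √(1 − r²)·e. A subject is removed if L > z, where z is the (1 − p) normal quantile, and is replaced.

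**Step 1: shift in mean change, no true effect.** Shift = −r·φ(z)/(1 − p).
- p = 0.02: z = 2.054, φ = 0.0484; 0.5 × 0.0484/0.98 = 0.025 SD
- p = 0.05: z = 1.645, φ = 0.1031; 0.5 × 0.1031/0.95 = 0.054 SD
- p = 0.10: z = 1.282, φ = 0.1755; 0.5 × 0.1755/0.90 = 0.097 SD

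At r = 1 these double to 0.049, 0.109 and 0.195 SD. All are toward improvement.

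**Step 2: multivariate time test.** One-sample Hotelling T² on 60 completers, with selection acting on one scale; simulated rejection in any direction at 0.05:

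| Scales | r | p = 2% | p = 5% | p = 10% |
|---|---|---|---|---|
| 8 | 0.5 | 5.3% | 5.7% | 7.1% |
| 8 | 1 | 5.3% | 7.1% | 15.7% |
| 2 | 0.5 | 5.3% | 6.2% | 9.6% |
| 2 | 1 | 6.0% | 10.9% | 30.7% |

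The inter-scale correlation is assumed, so I read the r = 0.5 rows no more finely than about 5% to 8% (eight scales) and 5% to 10% (two).

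**Step 3: wait-list t-test, 40 versus 20, no true effect.** With equal removal, the chance of a significant result favouring exercise stays at 2.4% to 2.6% against 2.5%. If the wait-list removal rate is half that of the exercisers, it is 2.8%, 3.1% or 3.7% at r = 0.5.

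**Step 4: a true difference of 0.5 SD, same removal threshold in both groups.** The mean change kept in a group with true mean μ is μ − r·φ(z − rμ)/Φ(z − rμ). Here p is the removal rate in the group with no effect.

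| True 0.5 SD | r | p = 2% | p = 5% | p = 10% |
|---|---|---|---|---|
| Benefit, as seen | 0.5 | 0.489 | 0.480 | 0.468 |
| Benefit, as seen | 1 | 0.466 | 0.432 | 0.390 |
| Harm of one intensity, as seen | 0.5 | 0.484 | 0.472 | 0.459 |
| Harm of one intensity, as seen | 1 | 0.422 | 0.372 | 0.319 |

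**The case against.** The strongest reply is that the comparison the hypothesis names is with a control group, and that comparison is nearly intact. Its error rate holds if removal is equal, and stays below 4% at r = 0.5 even if the wait-list is removed half as often. An uncontrolled time effect is weak evidence of benefit in any case. This stands, and it is why the point is modest. It does not dispose of it, because section 9.1 declares interest in the time effect and the between-group contrasts still shrink.

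The size rests wholly on assumed p and r. That also stands. At 2% to 5% and r = 0.5 the shift is 0.02 to 0.05 SD, which would rarely change a conclusion.

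Four stronger readings are tempting and not supported:
- A paired t-test on one scale with 60 pooled completers would show false improvement in 4% to 41% of trials against 2.5%, over r from 0.5 to 1. But section 9.1 plans MANOVA by category for secondary outcomes, and its only paired t-tests compare follow-up with the end of exercise.
- One might say that subjects are selected on the analysed score. Section 7.3 names no scale or cut-off, so r = 1 is a ceiling and not the expected case.
- One might infer that the wait-list comparison favours exercise, because training is supervised three times a week while the wait-list is contacted monthly (section 4.4.7). That is plausible, but mood is not among the items that session staff record (section 7.1).
- The argument does not carry to TMT-B or to adverse-event records. The completers-only set touches every outcome, but the one-directional selection shown here concerns mood and behaviour.

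**Conclusion.** The concern holds in a limited form. Removal for mood or behavioural worsening, replacement, and exclusion from analysis are all explicit, and nothing elsewhere repairs the combination. With no true effect, the pre-post mood change is biased toward improvement by about 0.02 to 0.10 SD at r = 0.5, and by at most about 0.20 SD at the ceiling. Inflation of the multivariate time test is small at r = 0.5. The wait-list comparison is valid under no effect if removal is equal across arms. A true 0.5 SD benefit would appear as about 0.49 to 0.47 SD at r = 0.5 (0.47 to 0.39 at r = 1), and a 0.5 SD harm of one intensity as 0.48 to 0.46 SD (0.42 to 0.32 at r = 1).

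These figures depend on assumed removal of 2% to 10%, the assumed r, normal scores and an inter-scale correlation of 0.5. The direction of the time bias does not depend on the exact values, provided worsening and scale change are positively correlated. It is worth correcting because the correction is cheap, not because it is likely to overturn the trial's findings.

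**What to change.** **Section 7.3.** Keep the safety rule: stop training and refer. Add that, with the subject's agreement and when clinically appropriate, the BDI-II and BSI-18 continue to be collected at the remaining scheduled visits.

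**Section 9.1.**
- Analyse mood and behavioural outcomes in all randomised subjects with a baseline and any scheduled later score, including those removed after a visit at which they were scored.
- Use baseline to 3 months for the initial exercise groups versus the wait-list. For the time model, use each subject's own pre- and post-exercise visits; for wait-listed subjects the post-exercise visit is at 6 months.
- Count replacements as additional subjects, not as substitutes for those removed.
- Tabulate removals by reason, arm and period.
- Rest any claim of mood benefit on the wait-list comparison, not on the time effect alone.
- Use a score taken at removal, or a worst-rank assignment, only in a sensitivity analysis. A score triggered by worsening is off schedule and probably near its worst. Either device may count against exercise if worsening is detected more often at supervised sessions.

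**Cost.** One sentence in 7.3, one paragraph in 9.1, and approval for continued contact with removed subjects. The two questionnaires take about 15 minutes per visit (under 5 plus about 10, section 4.4.2), for roughly 2 to 8 subjects at the assumed rates. Some will refuse or withdraw their data, as section 7.3 allows, and later scores may follow outside treatment.
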